8.1.3 Severity Assessment

AEs occurring during this study will be graded in accordance with the NCI CTCAE Version 5.0. Documentation of AE grading in the source documents and CRF should be consistent with provided definitions.

8.1.4 Causality

For each AE, the Treating Investigator will determine and document whether there exists a reasonable possibility that the study treatment caused or contributed to the AE. Potential attribution of an adverse event associated with trial therapy will be provided for all study drugs, sitravatinib and/or pembrolizumab. The Investigator's assessment should be recorded in the source document. The CRF will provide the options for attribution to each study treatment as “related” or “not related.” If the Investigator's causality assessment is “unknown but not related to investigational product,” this should be recorded in the CRF as “not related.” If the Investigator does not know whether or not the study treatment is causally related to the event, reporting for study purposes will be as “related” to study treatment.

8.1.5 Expectedness

The Treating Investigator will be responsible for determining whether an AE is expected or unexpected. An AE will be considered unexpected if the nature, severity, or frequency of the event is not consistent with the risk information listed in the reference safety information. Reference safety information is the US Package Insert for pembrolizumab and the most current version of the Investigator's Brochure for Sitravatinib.

8.2 Serious Adverse Events

A Serious Adverse Event (SAE) is any event that meets any of the following criteria:

- Results in death
- Is life-threatening (immediate risk of death)
- Requires inpatient hospitalization or prolongation of existing hospitalization
- Results in persistent or significant disability/permanent damage (substantial disruption of the ability to conduct normal life functions)
- Results in congenital anomaly/birth defect
- Other: Important medical events that may not result in death, be life-threatening, or require hospitalization, may be considered an SAE when, based upon appropriate medical judgment, they may jeopardize the patient and may require medical or surgical intervention to prevent one of the outcomes listed in this definition. Examples of such events are: Intensive treatment in an emergency room or at home for allergic bronchospasm; blood dyscrasias or convulsions that do not result in inpatient hospitalization; development of drug dependency or drug abuse

8.3 Reporting of AEs and SAEs

8.3.1 Reporting Period

Please refer to the Manual of Procedures (MOPs) for SAE reporting procedures.

The reporting period for non-serious AEs begins from the day of the first dose of study treatment and continues until at least 28 days after last administration of study treatment, or until resolution of AEs to Grade 0-1. If a patient begins a subsequent anticancer therapy the AE reporting period ends at the time the new treatment is started. Signs and symptoms of the patient's cancer diagnosis and/or comorbidities present prior to the first dose of study treatment should be noted and recorded separately (not as an AE).

The active reporting period for SAEs begins from the time that the patient provides informed consent (i.e., prior to undergoing any study-specific procedure or assessment) and continues until at least 28 days after the last administration of study treatment. All SAEs ongoing at the end of treatment should be followed until they have resolved or stabilized to a chronic condition, whichever is later. If a patient begins a subsequent anticancer therapy, the reporting period for new SAEs ends at the time the new treatment is started. Serious adverse events occurring after the active reporting period has ended should be reported to Mirati if the Treating Investigator becomes aware of them and if the Sponsor Investigator

assesses at least a reasonable possibility of being related to study treatment. These SAEs should be followed until resolved or stabilized to a chronic condition.

8.3.2 Reporting Requirements

Please refer to the Manual of Procedures (MOPs) for SAE reporting procedures.

All AEs (including SAEs) must be documented in source documents and reported in the CRF. Please note that the CRF and SAE report forms may collect information in somewhat different formats. Where the requested data overlap in different formats, the information should be consistent between the two forms.

All SAEs will be reported to the Sponsor Investigator within 24 hours of becoming aware of the event. Local investigators will complete the provided SAE form and send to the assigned Project Manager and Sponsor Investigator via email. The Sponsor Investigator will review the event and determine final attribution to study treatment. The Sponsor Investigator is responsible for expedited reporting to the FDA, when required, including meeting all timelines. Each site is responsible for following local procedures for submitting SAEs to the IRB of record.

8.3.3 SAE reporting to Mirati Therapeutics Inc.

For patients who sign the study informed consent form (ICF), SAE collection starts at time of main study informed consent whether the patient is a screen failure or not. The Sponsor, by way of the assigned Project Manager, is also required to notify Mirati Therapeutics, using the contact details supplied in Section 8.3.4. within 24 hours/1 business day of learning of its occurrence. Follow-up information is sent to the same contact(s) to whom the original SAE Report Form was sent, using a new SAE Report Form stating that this is a follow-up to the previously reported SAE and giving the date of the original report. Each re-occurrence, complication, or progression of the original event should be reported as a follow-up to that event regardless of when it occurs. The follow-up information should describe whether the event has resolved or continues, if and how it was treated, whether the blind was broken or not, and whether the patient continued or withdrew from study participation.

If the SAE is not previously documented in the Investigator's Brochure or Package Insert (new occurrence) and is thought to be related to the study treatment, the Sponsor, by way of the assigned Project Manager, will send a notification to Mirati Therapeutics, as it sees appropriate, who may need to issue an Investigator Notification (IN), to inform all Investigators involved in any study with the same drug that this SAE has been reported. Suspected Unexpected Serious Adverse Reactions (SUSARs) will be collected and reported to the competent authorities (except FDA as Sponsor is responsible for reporting) and relevant ethics committees.

Mirati Therapeutics Contact:

Mirati Therapeutics

Email: [contact]

[contact]

Phone (for fax issues): [contact]

Investigative site must also indicate, either in the SAE report or the cover page, the causality of events in relation to all study medications and if the SAE is related to disease progression, as determined by the principal investigator.

All SAEs have to be reported to Mirati Therapeutics, whether or not considered causally related to the investigational product. All SAEs will be documented. The investigator is responsible for informing the IRB and/or the Regulatory Authority of the SAE as per local requirements.

8.3.4 Reporting of SUSARs to Yale Cancer Center

Mirati Therapeutics will forward SUSARs occurring with Sitravatinib to the Yale Cancer Center in the following timelines:

- Reports of fatal or life threatening Serious Adverse Drug Reactions will be sent within five (5) calendar days of Receipt Date.
- Reports of Serious Adverse Drug Reactions (other than fatal or life threatening) will be sent within twelve (12) calendar days of Receipt Date.

8.3.5 Reporting to the FDA

This study will be conducted under an IND (Investigational New Drug application) that will be held by [name]. The Sponsor Investigator, by way of the assigned Project Manager and the IND/IDE Management Office, will report in an expedited manner all SAEs meeting the criteria of “serious”, “unexpected” and “related to study treatment”. Written safety reports will use a MedWatch Form 3500A. A “fillable pdf” version with instructions is available at: http://www.fda.gov/medwatch/safety/FDA-3500A_Fillable_08-16-2006.pdf

There are two types of expedited safety reports to the FDA:

1. **7-Calendar-Day FDA Telephone or Fax Report:** The sponsor-investigator will directly notify the FDA, within 7 calendar days after his initial receipt of the information, of any adverse event that is ALL of the following:

Death or immediately life-threatening
Unexpected
Associated with the use of study drug

Notification to the FDA will be made directly to the new drug review division in the Center for Drug Evaluation and Research or in the product review division for the Center for Biologics Evaluation and Research, whichever was responsible for the review of the IND.
[21CFR312.32(c)] A written report of the event is to follow within 8 calendar days from the submission of the initial report.

2. **15-Calendar-Day FDA Written Report:** The sponsor-investigator will directly notify the FDA within 15 calendar days of any adverse event that is ALL of the following:

Serious (due to non-fatal and non-life threatening criteria)
Unexpected
Associated with the use of study drug

Note: Serious Adverse Events which do not meet the criteria for expedited reporting will be reported to the FDA in the IND Annual Report.

8.4 Reporting of Pregnancy and Lactation

Exposure during pregnancy (i.e., exposure in-utero [EIU]) may occur in a female study participant, or the female partner of a male study participant if:

- A female becomes or is found to be pregnant during treatment or within 6 months after discontinuing treatment or having been directly exposed to the investigational product;
- A male is exposed to the investigational product within 6 months of conception or during the pregnancy of his partner.

If EIU occurs, the subject will immediately be removed from the study. The site will contact the subject at least monthly and document the subject's status until the pregnancy has been completed or terminated. The outcome of the pregnancy will be reported to the Sponsor Investigator and Mirati without delay and within 24 hours to the Sponsor Investigator if the outcome is a serious adverse event (e.g., death, abortion, congenital anomaly, or other disabling or life-threatening complication to the mother or newborn).

The study investigator will make every effort to obtain permission to follow the outcome of the pregnancy and report the condition of the fetus or newborn to the Sponsor Investigator and Mirati. If the outcome of the pregnancy meets the criteria for an SAE (i.e., ectopic pregnancy, spontaneous abortion, intrauterine fetal demise, neonatal death, or congenital anomaly), an SAE report should be submitted to Sponsor Investigator and Mirati.

8.5 Safety Reporting and Monitoring (DSMP)

8.5.1 Data and Safety Monitoring Committee

The Yale Cancer Center (YCC) Data and Safety Monitoring Committee (DSMC) will provide the primary oversight of data and safety monitoring. The Yale DSMC will review and monitor compliance, toxicity and deviations from this study. The committee is composed of clinical specialists with experience in oncology and who have no direct relationship with the study. Information that raises any questions about participant safety will be addressed with the Sponsor Investigator.

The DSMC will review this protocol bi-annually, at a minimum. Information to be provided to the committee includes: a study narrative by the PI, a summary DSMC report (which includes participant accrual, response, trial status history, SAEs, adverse events, deviations and survival); audit results, and monitoring reports, as applicable. Other information (e.g., scans, laboratory values, etc.) will be provided upon request. Upon completing the review, the DSMC will approve whether the study should continue as planned, require modification/amendment, or be placed on administrative hold with accrual temporarily suspended.

Trials being monitored by the YCC DSMC will remain under the YCC DSMC purview until a DSMC review has occurred that includes the research activity of the last subject who completed the intervention, or until the DSMC feels there are no patient safety concerns that require further monitoring. The DSMC will determine the length of continued DSMC review.

The DSMC has authority to intervene in the conduct of these studies as necessary to ensure the safety of the participants and to maintain the highest quality in the clinical research performed at YCC. The DSMC has the authority to require additional monitoring and/or more frequent reporting on study progress and serious adverse events.

8.5.2 Study Site Monitoring

Study site monitoring is necessary to assure adequate protection of the rights of human subjects and the safety of all subjects involved in clinical investigations and the quality and integrity of the resulting data submitted.

The Sponsor-Investigator-designated monitor(s) conducts monitoring visits to ensure that clinical investigators and study team members are compliant with the protocol, ICH good clinical practice, federal, state and local regulations and institutional policies and procedures, that data are of high quality and integrity, and that the facilities and staffing are adequate for continued study participation. This will be performed by conducting monitoring visits including a site initiation visit, regularly scheduled interim monitoring visits and/or remote interim monitoring visits while subjects are on study, and a site close-out visit at Choose an item.. Following each site visit, a visit report will be generated containing information on site activities and a summary of pertinent points and action items. The report will be provided with a follow-up letter. Site-specific data status reports will be distributed to the site regularly

to outline planned, missing or incomplete case report forms and any outstanding data queries.

During monitoring visits, the following may be reviewed:

- Protection of the rights, safety and welfare of subjects through review of informed consent/informed consent process and documentation, adverse events (AEs) and serious adverse events (SAEs) and safety procedures
- Subject eligibility
- Source verification
- Protocol compliance
- Deviations and Non-compliance
- Investigator Site File
- GCP compliance
- If applicable, include: Investigational Drug/ Device Storage and Accountability (including quantity and disposal procedures)
- If applicable, include: Laboratory Facilities
- If applicable, include: Equipment maintenance and calibration
- Additional study supplies inventory and assessment
- Study progress and/or follow-up on issues with Site Principal Investigator (PI) and relevant members of the study team

The Sponsor-Investigator and YCCI will define the required study monitoring activities in a Study Monitoring Plan.

9 STATISTICS

9.1 Statistical Methods

9.1.1 Statistical Design

This is a Phase 2 trial of the novel therapeutic sitravatinib in combination with pembrolizumab for the first-line treatment of patients with PD-L1 positive non-squamous metastatic NSCLC. The primary endpoint of this study is ORR as defined by RECIST 1.1, for patients treated with this combination. This study will enroll patients into two cohorts defined by PD-L1 status: PD-L1 TPS \geq 50% and TPS 1-49%. We will implement a Simon's Two-Stage Design to evaluate the efficacy of sitravatinib in combination with pembrolizumab for each cohort separately.

Each cohort will contain 35 patients, for a total of 70 patients (see discussion of sample size calculation below, section 9.1.3). Within each cohort, 30 patients will comprise the “main

study population" or Group A (see Study Schema 4.1), who will receive sitravatinib and pembrolizumab in combination starting on C1D1 of the study. It is hypothesized that this combination will result in at least 25% improvement in ORR when compared with historical control ORR of 39% for TPS \geq 50% and 17% in TPS 1-49%(6). Secondary endpoints include OS, PFS, Duration of Response (DOR) and Clinical Benefit Rate (CBR) in this population.

Initially patients will be randomized until five patients from each cohort have been assigned to Group B (to receive a 3-week run-in with pembrolizumab alone followed by the addition of sitravatinib on C2D1). The patients from this "pembrolizumab run-in" group, or Group B (see Study Schema 4.1), will not be included in the main statistical analysis of the primary endpoint. ORR, OS, PFS, DOR and CBR in Group B will be analyzed separately and will be secondary endpoints for this study.

9.1.2 General Analysis Plan

In general, summary statistics will be presented as percentages in the case of categorical variables and as means with standard deviations in the case of continuous variables. When applicable, t-tests or Wilcoxon rank-sum tests will be used to make comparisons between responders and non-responders, depending on the distribution of data. Paired t-tests or Wilcoxon signed-rank tests will be used to compare continuously distributed markers measured at different time points. Chi-square tests or Fisher's exact tests will be used to make comparisons between patient subgroups of interest for categorical variables. Summaries of safety data will be tabulated. Additional summaries or listings of adverse events for AEs of special interest may also be provided if appropriate. All analyses will be done separately for Cohorts A and B.

9.1.3 Sample Size Considerations

In Group A, for the cohort with TPS \geq 50%, we intend to enroll a maximum of 30 evaluable patients using Simon's minimax design. The sample size calculation is based on the desire to discriminate a promising ORR of 64% from a disappointing ORR of 39%(6). At stage 1, 17 subjects will be entered on the study. If \leq 7 responses are seen, the study will be terminated. At stage 2, 13 additional subjects will be entered. At the end of stage 2, if 16 or more subjects experience a response, the combination will be considered worthy of further study. *This design yields a type I error rate of 0.07 and power of 90% when the true response rate is 64%.*

In Group A, for the cohort with TPS 1-49%, we intend to enroll a maximum of 30 evaluable patients using the admissible two-stage design. The sample size calculation is based on the desire to discriminate a promising ORR of 42% from a disappointing ORR rate of 17%.(6) At stage 1, 16 subjects will be entered on the study. If ≤ 3 responses are seen, the study will be terminated. At stage 2, 14 additional subjects will be entered. At the end of stage 2, if 9 or more subjects experience a response, the combination will be considered worthy of further study. *This design yields a type I error rate of 0.05 and power of 91% when the true response rate is 42%.*

9.2 Efficacy Endpoints Definition and Analyses

9.2.1 Analysis Population

All of the patients who met the eligibility criteria (with the possible exception of those who received no study medication) will be included in the main analysis of the response rate and the other efficacy analyses. Conclusions will be based on all eligible patients. Sub analyses may then be performed on the basis of a subset of patients, excluding those for whom major protocol deviations have been identified (e.g., early death due to other reasons, early discontinuation of treatment, major protocol violations, etc.). However, these sub analyses may not serve as the basis for drawing conclusions concerning treatment efficacy, and the reasons for excluding patients from the analysis should be clearly reported.

Safety analysis will be performed on all patients who receive at least one dose of study treatment.

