(1) To evaluate ORR, OS, PFS, DOR, and CBR in patients with advanced, non-squamous, treatment naïve, PD-L1 positive NSCLC who receive pembrolizumab run-in followed by pembrolizumab/sitravatinib combination therapy.

(2) To evaluate the CNS activity of sitravatinib/pembrolizumab in patients with advanced, treatment naïve, PD-L1 positive NSCLC by measuring Intracranial Objective Response Rate (iORR) and Intracranial Duration of Response(iDOR) in patients with baseline CNS disease, and Intercranial Progression-Free Survival (iPFS) in all patients.

(3) To study correlates of the adaptive and innate immune responses induced by sitravatinib and pembrolizumab treatment in both tumor tissue and peripheral blood.

(4) To explore the association between tumor immune contexture and clinical benefit to sitravatinib and pembrolizumab.

Study Duration

4 Years

Summary of Study Design

This is a multicohort phase 2 study to evaluate the efficacy of pembrolizumab combined with the investigational drug sitravatinib in the frontline treatment of advanced, non-squamous PD-L1 positive NSCLC. For clinical analysis, there will be two patient cohorts defined by PD-L1 status: Cohort 1 for patients with PD-L1 Tumor Proportion Score (TPS) 1-49% and Cohort 2 for patients with TPS \geq 50% using the FDA approved 22c3 PD-L1 IHC assay or a local assay performed in a CLIA facility. We will implement a Simon's two-stage design to evaluate the efficacy of sitravatinib in combination with pembrolizumab for each cohort separately.

There will be two groups within each cohort of this study: the "main study population" (Group A) in which patients will receive pembrolizumab plus sitravatinib beginning on Cycle 1 Day 1 (C1D1), and a "pembrolizumab run-in population" (Group B) in which patients will receive

pembrolizumab alone for 1 dose followed by pembrolizumab plus sitravatinib beginning C2D1.

The primary endpoint of the trial is the ORR for patients treated with pembrolizumab plus sitravatinib in the main study population. The purpose of the pembrolizumab run-in population is to obtain tissue and blood samples from these patients to be used as controls for correlative studies and to determine the preliminary efficacy of pembrolizumab alone followed by the combination.

Number of Study Sites

Up to 2 sites

Study Population

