4.5 Study Population

4.5.1 Number of Participants

This study will plan to enroll a maximum of 35 evaluable patients to each cohort for a total of 70 study participants. 30 patients from each cohort will be enrolled to Group A and 5 patients from each cohort will be enrolled to Group B (see Trial Schema Section 4.1). In order to accrue 70 evaluable patients, we expect to screen 80 patients (~10% ineligibility rate). The randomized portion of the study will be performed exclusively at Yale, after which time we expect a roughly equal enrollment between the 2 sites.

4.5.2 Inclusion Criteria:

In order to be eligible to participate in this study, an individual must meet all of the following criteria:

1. Histologically or cytologically confirmed non-squamous NSCLC that is metastatic (Stage IV), recurrent, or unresectable locally advanced (Stage IIIB/IIIC) disease, not amenable to treatment with curative intent.

2. No prior systemic therapy for advanced disease. Prior chemotherapy for local or locally advanced disease is allowed if completed >6 months prior to trial enrollment. Prior immunotherapy is not allowed.
3. PD-L1 \geq 1% using the 22c3 PD-L1 IHC assay or a local assay performed in a CLIA facility
4. Age \geq 18 years.
5. Eastern Cooperative Oncology Group (ECOG) performance status 0 or 1.
6. Life expectancy of at least 3 months.
7. Measurable disease as per RECIST v1.1
8. Adequate bone marrow and organ function demonstrated by:
 - a. Absolute neutrophil count \geq 1,500/mm³ ($1.5 \times 10^9/L$).
 - b. Hemoglobin \geq 8.0 g/dL not dependent on transfusion support.
 - c. Platelet count $\geq 75 \times 10^9/L$ ($\geq 75,000$ per mm³).
 - d. Alanine aminotransferase (ALT) and aspartate aminotransferase (AST) $\leq 1.5 \times$ ULN without liver metastases; $< 5.0 \times$ ULN if documented liver metastases
 - e. Serum total bilirubin \leq ULN, or for patients with potential Gilbert's, direct bilirubin \leq ULN
 - f. Calculated creatinine clearance \geq 40 mL/min, using the Cockcroft-Gault formula.
9. Women of child-bearing potential (WOCBP) or men whose partner is a WOCBP agrees to use contraception while participating in this study, and for a period of 6 months following termination of study treatment.
10. Completed informed consent process, including signing IRB approved informed consent form.
11. Willing to comply with clinical trial instructions and requirements.

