9.3 Safety Analysis

Evaluation of the safety and toxicity profile of the combination of sitravatinib and pembrolizumab in the first-line treatment of patients with non-squamous metastatic NSCLC is a secondary objective in this study. Secondary endpoint is adverse events as per CTCAE v.5. The Safety population is defined as all patients who received any dose of study treatment (i.e., sitravatinib and/or pembrolizumab) and will be used for all safety analyses.

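### Does the loosely worded response analysis set (Section 9.2.1) leave the two-stage response counts without a usable denominator?

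*Combined protocol and SAP*

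**What the plan says.** Five places bear on who is counted for the primary objective response rate (ORR).

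- **Synopsis, Summary of Study Design:** "The primary endpoint of the trial is the ORR for patients treated with pembrolizumab plus sitravatinib in the main study population".
- **Section 9.1.1:** "The primary endpoint of this study is ORR as defined by RECIST 1.1, for patients treated with this combination".
- **Section 9.2.1**, the only section headed as the analysis population, opens the main response analysis to "All of the patients who met the eligibility criteria (with the possible exception of those who received no study medication", the last group in parentheses. The next sentence reads "Conclusions will be based on all eligible patients". It then allows subset analyses that leave out major deviations, including early discontinuation, and bars them from supporting efficacy conclusions.
- **Section 9.1.3**, for each cohort: "we intend to enroll a maximum of 30 evaluable patients". The stages are counted in subjects entered; for TPS ≥50%, "At stage 1, 17 subjects will be entered on the study". Section 4.5.1 uses the same undefined word: "In order to accrue 70 evaluable patients, we expect to screen 80 patients".
- **Section 9.3**, for safety only: "The Safety population is defined as all patients who received any dose of study treatment (i.e., sitravatinib and/or pembrolizumab".

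Section 9.2.2 defines ORR in Group A as a percentage of patients and names no further condition.

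**The concern.** A two-stage design applies fixed response counts to fixed numbers of patients: 17 then 30 in the TPS ≥50% cohort, 16 then 30 in the TPS 1–49% cohort. The texts appear to treat two kinds of Group A patient differently.

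1. **Eligible, never dosed.** Section 6.4 allows up to seven days from randomization to treatment, so such a patient can arise. Counted among all eligible patients, this person fills a place and cannot respond. Counted only if treated, the place stays open for someone who can.
2. **Given pembrolizumab, never took sitravatinib.** This patient stays in under Section 9.2.1, but a literal reading of the Synopsis would take the patient out. The patient can respond, so the numerator could change.

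The trial is unblinded and response is read by the investigator. A denominator left open could therefore be settled after responses are known, and near a boundary that could turn a failure into a success or the reverse.

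**Working it through.** **Inputs (Section 9.1.3).** TPS ≥50%: p0 = 0.39, p1 = 0.64, n1 = 17, stop at r1 = 7 or fewer, n2 = 13, success at R = 16 or more of 30. TPS 1–49%: p0 = 0.17, p1 = 0.42, n1 = 16, stop at r1 = 3 or fewer, n2 = 14, success at R = 9 or more of 30.

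**Step 1: reproduce the plan.** With b the binomial probability,

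P(success) = Σ over x from r1+1 to n1 of b(x; n1, p) × P[Bin(n2, p) ≥ R − x].

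- TPS ≥50%: 0.0723 at p0 and 0.9006 at p1. The plan states 0.07 and 90%.
- TPS 1–49%: 0.0499 at p0 and 0.9136 at p1. The plan states 0.05 and 91%.

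**Step 2: undosed patients keep their places.** Each has no chance of response, so n1 (or n2) drops by one per patient and the bounds stay. The numbers of such patients are assumptions.

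| Undosed | Stage | TPS ≥50%: type I error / power | TPS 1–49%: type I error / power |
|---|---|---|---|
| 0 | – | 0.072 / 0.901 | 0.050 / 0.914 |
| 1 | 1 | 0.050 / 0.851 | 0.040 / 0.885 |
| 1 | 2 | 0.054 / 0.869 | 0.042 / 0.899 |
| 2 | 1 | 0.033 / 0.782 | 0.031 / 0.847 |
| 2 | 2 | 0.038 / 0.824 | 0.035 / 0.880 |

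**Step 3: undosed patients are replaced.** Every counted place holds a dosed patient, and the figures are those of Step 1.

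**Step 4: the choice is made late.** Take one sequence of dosed patients. Without a refill in stage 1 of the TPS ≥50% cohort, success needs at least 8 responses in the first 16 and at least 16 in 29. With the refill it needs at least 8 in the first 17 and at least 16 in 30. Any sequence that passes without the refill also passes with it. Taking the more favourable handling after seeing the data therefore gives at most the refilled type I error, 0.072. The same nesting holds at 0.050 in the other cohort. Going beyond 30 dosed patients with the bounds unchanged would raise type I error (0.093 and 0.058 with one extra patient), but Section 9.1.3 sets 30 as the maximum.

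**Step 5: the pembrolizumab-only patient.** Section 9.2.1 contemplates leaving out only patients who received no study medication, so this patient stays in. To size the alternative, suppose one such patient in stage 2, responding at p0, were swapped for a patient on the combination. The decision differs only if stage 1 is passed, the other 29 give exactly R − 1 responses, and the two patients' outcomes differ, which has probability p0(1 − p) + (1 − p0)p.

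- TPS ≥50%: 0.0470 × 0.4758 = 0.022 at a true ORR of 39%; 0.0492 × 0.5308 = 0.026 at 64%.
- TPS 1–49%: 0.0465 × 0.2822 = 0.013 at 17%; 0.0348 × 0.4472 = 0.016 at 42%.

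**Step 6: the reported interval.** With two undosed patients dropped and not replaced, 17/30 has an exact 95% interval of 37.4–74.5%, which includes 39%, while 17/28 has 40.6–78.5%, which does not. At 16 responses both intervals include 39% (34.3–71.7 and 37.2–75.5). At 18 both exclude it (40.6–77.3 and 44.1–81.4). The interval is not the decision rule, and 17 responses pass that rule either way.

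**The case for a change.** The strongest case for a change is that the fix costs a few words, while one undosed patient left in stage 1 of the TPS ≥50% cohort costs about five points of power (0.901 to 0.851). It also raises the chance of stopping a truly promising combination at stage 1 from 4.6% to 7.9%. Results exactly at the boundary carry half of the type I error in that cohort (0.036 of 0.072) and 58% in the other (0.029 of 0.050), so one patient in or out can decide the outcome.

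Part of this stands. The exception for undosed patients is left as a possibility, *evaluable* is undefined, and the power figures are right for the case assumed.

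The rest is weaker. The Synopsis and Section 9.1.1 sentences describe the regimen and separate Group A from the run-in group; they do not set up a rival analysis set. Within Section 9.2.1 the second sentence reads naturally as shorthand for the first, set against the subset analyses that follow. The shares at the boundary are not the chance that the ambiguity changes a decision. For the pembrolizumab-only patient that chance is 1.3% to 2.6%, given that such a patient exists and the place is refilled, and Section 9.2.1 already settles the case. Undosed status is also normally known within days of enrolment, well before the first scan at six weeks.

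**Conclusion.** No change is needed. The remaining gap is whether an eligible, never-dosed Group A patient is counted or replaced, and the documents point an analyst to a sensible answer. The endpoint is described for treated patients, Section 9.2.1 names this one group as a possible exclusion, and Section 9.2.3 times progression-free survival from first dose and overall survival from treatment start, so an undosed patient has no time origin. Leaving such patients out and filling the place keeps the stated error rates. Keeping them in is conservative: type I error falls, and one such patient costs about 3 to 5 points of power in the TPS ≥50% cohort and 1.5 to 3 points in the TPS 1–49% cohort. Neither handling, nor a late choice between them, raises type I error above 0.072 and 0.050.

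This rests on the bounds and the cap of 30 being kept, and on undosed patients being few. The documents give no rate, and two in stage 1 of the TPS ≥50% cohort would lower power to 0.782. Tidier wording would be welcome at a routine amendment, but the design, the decision rule and the interpretation do not depend on it.
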